2.1 Background

Oesophageal cancer is the sixth most common cause for cancer related deaths with over 450,000 new cases and 400,000 resulting deaths per year globally. Most cases in the UK are adenocarcinoma with some of the poorest outcomes from this cancer type in Europe -- mainly

due to late diagnosis. The main risk factor is chronic reflux disease and due to the high prevalence and non-specific nature of these symptoms most patients are managed with acid-reflux (PPI) medication without referral for endoscopy. For those patients that are referred the endoscopy is normal in over 70% of cases, and there is not enough capacity for endoscopy especially considering colon cancer screening.

2.2 Innovation

The Cytosponge-TFF3 test is a disruptive technology developed by Cambridge University that could revolutionise the clinical care pathway for reflux disease, which is a risk factor for adenocarcinoma. This device has been shown to be safe and acceptable to patients in studies involving >4,000 individuals across 3 continents and a randomised study of over 13,000 eligible individuals on PPI medication to identify Barrett's oesophagus has just been successfully completed¹. This innovation could focus procedures on those at greatest risk of cancer - especially relevant since we have effective, NICE approved endoscopic interventions for early oesophageal cancer. Through improved diagnosis we can also reduce the over-use of proton pump inhibitor (PPI) medication which is expensive with long-term side-effects. Health economic modelling studies have shown that this is a cost-effective solution falling below the NICE threshold. It would also be possible to implement Cytosponge for individuals at risk for squamous cell carcinoma of the oesophagus. The device has been licensed to Covidien GI Solutions, now Medtronic by the MRC. A new Early Detection company called Cyted has been spun out from the University of Cambridge and is providing quality assured processing of Cytosponge with AI solutions for economic high throughput (Company Number: 11478299).

2.3 Main Aims

2.3.1 Work package 1

Mine electronic health records and endoscopy databases at a national level to improve identification of individuals at increased risk of oesophageal cancer

2.3.2 work package 2

Build a transferrable operating model for a nurse-lead Cytosponge clinic

2.3.3 Work package 3

Implement Artificial Intelligence algorithms for high throughput computational pathology for the Cytosponge-TFF3 test and endoscopic biopsies. Samples/data collected from newly recruited patients will feed this activity.

2.3.4 Work package 4

Health economic and implementation research to assess effectiveness of the novel pathway including user preferences for patients and clinicians. Data collected from newly recruited patients will feed this activity.

2.4 Vision

To re-design and evaluate the clinical pathway such that we systematically identify those at risk, perform a simple test to inform who needs endoscopy and in so doing rationalise the use of long-term PPI medication. Due to the cost-effectiveness of Cytosponge-TFF3 compared with endoscopy these changes will likely result in an economic benefit to the NHS, a social benefit for early detection of a lethal cancer and a reduction in over-use of PPI medication.

3 Summary Work Package 1

- **Objective** To derive and evaluate a risk prediction tool to predict oesophageal cancer (all types and according to squamous or adenocarcinoma subtype) which can be applied in primary care to identify high risk patients suitable for assessment with the Cytosponge in primary care.
- Design Prospective population based open cohort study using routinely collected data from 1500 GP practices in England in the QResearch database (derived from EMIS electronic medical records) between 01.01.2000 and 31.12.2020 (or latest data available). We will use the QResearch database to develop the risk equations. Models will be developed on a derivation dataset from a subset of approximately 1100 practices and validated in the remaining 400 practices. The model will be externally evaluated in other relevant datasets as they become available.
- Subjects We will study adults aged 40 years and over who are free of oesophageal cancer at study entry. Patients with a new onset of alarm symptoms (e.g. dysphagia, weight loss etc) in the preceding 3 months will also be excluded.
- Methods Cox time-to-event models will be used in the derivation data to derive separate risk equations in males and females for estimating risk of oesophageal cancer. Predictors considered will include age, ethnicity, deprivation, smoking status, alcohol intake, body mass index, pre-existing medical co-morbidities, and concurrent medication. Measures of performance (prediction errors, calibration and discrimination) will be determined in the validation data for men and women separately and by ten-year age group.
- **Outcome** Our primary outcome is oesophageal cancer defined as recorded on GP record or linked hospital, cancer registry or death certificate.

4 Background

4.1 Clinical need

5.1.1 Epidemiology of oesophageal cancers

Oesophageal cancer is the 8th most common cancer and one of the deadliest cancers in the world². Although oesophageal squamous cell carcinoma (OSCC) is the predominant histological type worldwide, oesophageal adenocarcinoma (OAC) is more common in developed countries such as United States, Australia, United Kingdom, and Western Europe².

Incidence of the cancer type OAC has increased 6-fold since the 1990s and carries a dismal prognosis. The UK has some of the worst outcomes from this disease in Europe. Clinical guidelines have focussed on minimising endoscopy referrals unless patients have "alarm symptoms" suggestive of cancer. Nevertheless, General Practice referral rates vary widely, and low endoscopy referral rates have been linked with poor outcomes from oesophageal cancer.

A major risk factor for this cancer is chronic heartburn caused by reflux. Three to six percent of individuals with reflux predominant symptoms may have the precursor lesion called Barrett's oesophagus, but only around 20% of patients with Barrett's are diagnosed. It is estimated that the burden of OAC could be reduced by up to 50% as a result of increasing the proportion of individuals with reflux symptoms who are investigated. This is a formidable task since heartburn symptoms affect between 5%-20% of the population and account for up to 10% of GP consultations. GPs therefore focus on controlling reflux symptoms with acid-suppressant medication, particularly proton pump inhibitor therapy (PPI). PPIs are highly effective, but patients often continue taking them life-long and there are increasing concerns about long-term side effects including osteoporosis, pneumonia^{3 4} and recently allergy³.

4.2 Introduction to DELTA

In 2008 the Chief Medical Officer, Sir Liam Donaldson, raised oesophageal cancer as a public health concern and identified an urgent need to develop a need for a safe, minimally invasive, affordable test applicable to the office setting to diagnose Barrett's oesophagus. Cambridge University have developed a new minimally invasive test for patients with reflux that can be performed in the GP surgery. This test is called CytospongeTM -TFF3 which has been tested in over 4,000 individuals across 3 continents.

Our vision is to re-design the clinical pathway for reflux. In primary care a new algorithm applied to NHS prescribing databases will flag symptomatic individuals at risk for oesophageal cancer to their GP. Individuals most at risk will be offered a Cytosponge[™] test in a nurse led clinic. The sample will be sent to a centralised laboratory for processing. The H&E and TFF3 stained cells collected by the Cytosponge[™] will be assessed using Artificial Intelligence to increase the throughput and reduce the cost. For cases with atypia detected by the

pathologist a p53 stain will be added. Individuals at high risk for cancer will be referred for endoscopy and PPI use will be rationalised.

Key innovations

Project DELTA

[figure not shown]

These changes could result in more efficient triage to endoscopy, an economic benefit to the NHS, a social benefit for early detection of a lethal cancer and a reduction in over-use of PPI medication.

4.3 Enhancing the primary care clinical pathway

Currently the clinical pathway for reflux in primary care relies on excluding alarm symptoms (e.g. dysphagia, weight loss) and managing reflux symptoms with acid-suppressant medication. The NICE guidelines recommend endoscopy via the 2 Week Wait pathway if alarm symptoms are present, and routine referral if the symptoms are persistent and occur in the context of other risks factors such as family history (CG27). If a patient is referred to secondary care via the routine pathway the vast majority of patients will be triaged straight to endoscopy. Clinic appointments in secondary care may be led by a dyspepsia nurse or a Gastroenterologist depending on the local policy and resources.

The current, conventional care pathway has a strong focus on triggering endoscopies which results in high costs for the NHS. Additionally, around 70% of these endoscopies are normal with no clinically significant finding (Endoscopy Service Report). The proposed, enhanced care pathway in this project implements a nurse/pharmacist-led clinic for patients with reflux predominant symptoms whereby a Cytosponge procedure is performed in a one-stop visit. This serves as an intermediate step in which the Cytosponge results, together with the high specificity of the test, are used to avoid unnecessary endoscopies.

The CytospongeTM can be readily placed into this pathway (see Fig). We propose that primary care individuals at high risk including those undergoing repeat prescriptions for reflux symptoms are considered for a CytospongeTM test, with more consideration given to their requirement for long term PPI medication as part of this process. The patients could be flagged electronically to a GP and the test performed by the practice nurse. Alternatively, with the expanding role of the community Pharmacist they would be ideally placed to perform this role. Thus, only patients deemed to be at risk for Barrett's oesophagus (or another oesophageal condition, or gastric IM) ascertained by the CytospongeTM test would be referred for endoscopy.

4.4 Introduction to cancer risk prediction tools

Over the last 10 years, [name] et al have developed, validated and implemented a novel set of risk prediction algorithms collectively known as the QCancer algorithms which predict the risk of different types of cancer using readily available information from routinely available electronic health records⁵⁻¹².

The first set of algorithms are designed to improve early diagnosis of an existing cancer on the basis of a combination of symptoms and readily available risk factors in order to identify those patients needing urgent investigation and referral⁵.

The second set of algorithms are designed to estimate longer term cancer risks in order to identify high risk asymptomatic patients with combinations of risk factors who might benefit from systematic screening or interventions to reduce their risk¹³.

This project provides the opportunity to introduce improvements to both sets of QCancer algorithms which are now possible due to the increased size of the QResearch database (which will enable us to distinguish between gastric and oesophageal cancer). It also provides an opportunity to explore risks associated with long-term medication use. For example, we can explore risks associated with proton pump inhibitors which are used to treat chronic reflux symptoms which could also potentially mask development of oesophageal cancer; use of NSAIDs which tend to increase reflux symptoms and use of medications such as aspirin^{14 15} or statins¹⁵ which may lower risk of oesophageal cancer on their own or in combination with PPI¹⁶ or cyclo-oxygenase inhibitors^{15 17}.

5 Objectives

The primary objective is to update and validate the QCancer algorithm to identify patients at highest risk of oesophageal cancer who may be suitable for assessment using the Cytosponge device.

Once developed and validated, we envisage that the updated algorithm could be used:

- 1. Within a consultation between the patient and a clinician with the intention of sharing the information with the patient to assess management options including assessment with Cytosponge
- 2. To electronically risk-stratify populations by applying the algorithm to all patients to then target and recall patients for a medication review and consideration of Cytosponge sponge assessment based on their levels of risk.
- 3. To inform mathematical modelling of the potential impact of changing the clinical pathway to include risk assessment +/- Cytosponge.
- 4. Adapted for use by the general public to improve communication and understanding of risk through implementation into web-based tools
- 5. Use by researchers to help generate new knowledge or insights.

6 Methods

6.1 Study design

We will undertake a cohort study in a large population of primary care patients using the latest version of the QResearch[®] database (currently version 45).

6.1.1 Data Sources

QResearch is a high-quality research database established in 2002 which has been used extensively for the development of risk prediction tools which are widely used across the NHS¹⁸⁻²³ as well as a wide range of high impact epidemiological research²⁴⁻²⁶. QResearch is a large, representative, validated GP practice research database nationally²⁷. The database is linked at an individual patient level to hospital admissions data (including intensive care unit data), cancer registrations and mortality records obtained from the Office for National Statistics. The records are linked using a project-specific pseudonymized NHS number. The

recording of NHS numbers is valid and complete for 99.8% of QResearch patients, 99.9% for ONS mortality records and 98% for hospital admissions records^{28 29}.

This project will use all four linked data sources (GP, hospital, mortality and cancer registry)

6.2 Study Population

6.2.1 Practice inclusion

We will include all practices in England who had been using their EMIS computer system for at least a year. We will randomly allocate three quarters of QResearch practices to the derivation dataset and the remaining quarter to a test (validation) dataset.

6.2.2 Patient inclusion

We will identify an open cohort of individuals aged 25-90 years who are registered with practices that have been contributing to QResearch for over 12 months on or after 1st January 2000 (study start date).

6.2.3 Patient exclusions

Exclusions will broadly match those for WP2 which aims to implement the risk algorithm for recalling patients for the Cytosponge and hence the following will be excluded

- Patients with a new onset of alarm symptoms (including haematemesis, unexplained weight loss, dysphagia) in the last 3 months before study entry since these are likely to require urgent referral on the 2-Week Wait pathway for endoscopy.
- Recorded diagnosis of a current or previous oro-pharynx, oesophageal or gastrooesophageal tumour
- Received prior surgical intervention to the oesophagus
- Recorded oesophageal varices, cirrhosis of the liver

Patients with recorded Barrett's oesophagus will be included and the presence of Barrett's oesophagus will be evaluated as a risk factor.

6.3 Study period

Patients will enter the cohort on the latest of the study start date or the date on which they become 25 or 12 months after registering with their GP practice. Patients will be followed up until they develop oesophageal cancer, die, leave the practice or the study end date or a maximum follow up period of 15 years.

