6.6.4 Co-morbidities and investigations

- 8. gastric cancer
- 9. Barrett's oesophagus*
- 10. Peptic ulcer disease*
- 11. Gastro-oesophageal reflux disease (including heart burn)
- 12. Type 1 and type 2 diabetes*
- 13. previous blood cancer*
- 14. previous breast cancer*
- 15. previous oral cancer*
- 16. previous pancreatic cancer*
- 17. Current H.Pylori infection (which may lower OAC risk)
- 18. pernicious anaemia
- 19. hiatus hernia
- 20. anaemia (including Haemoglobin values)
- 21. Full blood count
- 22. CT scan abdomen within the previous 5 years
- 23. CT scan pelvis within the previous 5 years
- 24. Barium meal/swallow within the previous 5 years
- 25. Endoscopy within the previous 5 years

All predictor variables will be based on the latest coded information recorded in the GP record prior to entry to the cohort.

6.7 **Descriptive analysis**

We will produce the following descriptive analyses for comparison with the literature and national statistics from the CRUK website.

- crude incidence of oesophageal cancer by age, sex, ethnicity, deprivation and calendar time.
- age standardised incidence of oesophageal cancer overall and by type.
- characteristics of cases diagnosed with oesophageal cancer age at diagnosis, stage, grade, histology, treatment (surgery, radiotherapy, chemotherapy, other).

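### The 15-year cap on follow-up biases the planned crude incidence by calendar time downward from 2015; the size depends on list turnover, which the protocol does not give

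*Protocol*

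**What the plan says.** - **Entry.** Section 6.2.2 defines an open cohort in practices contributing "on or after 1st January 2000 (study start date"). Section 6.3 adds: "Patients will enter the cohort on the latest of the study start date or the date on which they become 25 or 12 months after" registration with the practice.
- **Exit.** Section 6.3 states: "Patients will be followed up until they develop oesophageal cancer, die, leave the practice or the study end date or a maximum follow up period". It sets that maximum at 15 years and makes no provision for re-entry.
- **Study window.** Section 3 takes data "between 01.01.2000 and 31.12.2020 (or latest data available").
- **Descriptive rates.** Section 6.7 (Descriptive analysis) lists "crude incidence of oesophageal cancer by age, sex, ethnicity, deprivation and calendar time", and separately "age standardised incidence of oesophageal cancer overall and by type". It introduces them as "descriptive analyses for comparison with the literature and national statistics from the" CRUK website. Nothing in 6.7 exempts these rates from the cap in 6.3.

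**The concern.** An adult aged 25 or over who was registered by 1 January 1999, in a practice eligible from the start, enters on 1 January 2000. The cap then ends follow-up on one date for everyone in that group who has not already left. From 2015 the person-time comes from those who turned 25 after the start and those who registered later, and they are younger on average.

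The cap removes cases and person-years together, so a rate does not fall merely because people leave. It falls because those removed are older than those kept and so carry more than their share of the cases. The only calendar-time rate that 6.7 names is crude, so nothing in the stated analysis corrects for this. At stake is the trend over the six most recent years, in a series meant to be set beside national figures that have no such exit rule.

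**Working it through.** The protocol states no figure for this point, so there is none to reproduce. The dates come from the protocol; the size needs assumptions.

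**1. Dates.** 1 January 2000 + 15 years = 1 January 2015. From then to 31 December 2020 is six years.

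**2. Ages.** Minimum age at entry is 25 (section 6.2.2), so everyone removed on that date is at least 25 + 15 = 40. If the lower limit is 40, as section 3 has it, everyone removed is at least 55.

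**3. Direction.** Assume a stationary registered population in which leavers are replaced by new registrants of the same age, with annual turnover *t* equal at all ages. The share of those aged 40 or over in 2015 who have been under observation for 15 years is *s* = (1 − *t*)^15. Let *p* be the share of uncapped person-time, and *c* the share of uncapped cases, at age 40 or over. Then

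capped crude rate / uncapped crude rate = (1 − *s·c*) / (1 − *s·p*).

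This is below 1 whenever *c* > *p*, that is, whenever incidence rises with age. The protocol gives no age gradient, so the rise is an assumption.

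**4. Size.** A deterministic cohort model for ages 25-90, 2000-2020, assumed exponentially rising mortality, incidence proportional to between age³ and age⁵ and constant over time, and risk independent of entry date. At 3% turnover, *s* = 0.97^15 = 0.633. The lowest modelled shares kept are 55% of person-time and 38% of cases, which imply *p* = 0.45/0.633 = 0.71 and *c* = 0.62/0.633 = 0.98. Putting these into the formula:

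| Turnover a year | *s* | Person-time kept | Cases kept | Ratio | Fall |
|---|---|---|---|---|---|
| 3% | 0.633 | 0.55 | 0.38 | 0.69 | 31% |
| 5% | 0.463 | 0.67 | 0.55 | 0.81 | 19% |
| 8% | 0.286 | 0.80 | 0.72 | 0.90 | 10% |
| 10% | 0.206 | 0.85 | 0.80 | 0.93 | 7% |
| 15% | 0.087 | 0.94 | 0.91 | 0.97 | 3% |

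The full model agrees. The ratio is 1.00 up to 2014. From 2015 it is 0.65-0.94 for turnover of 3-10% and 0.97-0.98 for 15%. The lowest value, 0.65, arises when turnover is 12% in the young and declines to 3% in older people, because the stable registrants are then the oldest. At 3-10% turnover, mean age drops from 51.2 to between 44.7 and 49.8. A separate microsimulation, with turnover of 8-12% under age 45 and 3-8% above, gave ratios of 0.63-0.90.

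**5. Lower age limit of 40.** Ratios in 2015, for age³ and age⁵ gradients: 0.770 and 0.678 at 3% turnover; 0.855 and 0.797 at 5%; 0.922 and 0.890 at 8%; 0.947 and 0.925 at 10%; 0.979 and 0.971 at 15%. The direction does not depend on which age limit applies.

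**6. What does not move.** In the same model the age-standardised rate with the cap, divided by that without it, is 1.000 in every scenario. Age-specific rates do not change either.

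**The case against.** Several objections have force, and they limit the point.

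- **Retention is not documented.** The only follow-up length given is the 1.74-year mean in section 6.8.9. Read as an exponential mean, exp(−15/1.74) = 0.02% would reach 15 years and there would be no fall. But it is a sample-size input, and on the same reading only exp(−10/1.74) = 0.3% would reach 10 years, where section 6.8.6 plans Kaplan-Meier calibration by tenth of risk. It is a weak guide to retention in this cohort.
- **The exit may not be one cliff.** If eligibility in later-joining practices starts later (sections 6.2.1 and 6.2.2), exits are staggered. People who registered during 1999 enter during 2000 and stay into 2015. This smooths the step but does not reverse it.
- **A true trend may hide it.** Section 4.1 reports a 6-fold rise in adenocarcinoma since the 1990s. The models above assume no trend, so a visible fall is not assured.
- **The bullet in 6.7 could be read as age by calendar time.** Rates tabulated that way would be largely free of the problem. The wording allows this reading but does not require it.

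A reader might infer that the incidence results as a whole cannot be compared with national statistics, or that the comparison is a check on case ascertainment that would now mislead. The protocol supports neither. Age-standardised and age-specific rates are essentially unaffected, and 6.7 gives no purpose beyond comparison. Nor is there evidence for a further bias, after standardisation, from selecting people who moved practice recently; the model assumes none and the protocol gives no figure for one.

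**Conclusion.** The point holds for one planned output: crude, all-age incidence by calendar time. As written, sections 6.3 and 6.7 together bias that series downward from 2015, relative to its own earlier years and to national figures. The date follows from the protocol. The direction needs only that incidence rises with age and that some 2000 entrants remain under observation at 15 years. The size rests on assumed turnover, mortality and age gradient: roughly 6-35% at 3-10% turnover a year and 2-3% at 15%.

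It would be wrong to extend this to the prediction work. The 10-year risk equations in section 6.8.5 lie within the 15-year cap. Table 2 has no calendar dimension and reports age-standardised rates, so it is not materially affected either. This is a minor, descriptive-only improvement.

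**What to change.** In section 6.7, state that incidence by calendar time uses person-time from entry to cancer, death, leaving the practice or study end, without the 15-year maximum, and report it age-standardised or age-specific by calendar year. In the model, lifting the cap brings the ratio back to 1.00 in every year. A simpler alternative is to end the crude calendar-time series at 2014.

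Keep the cap for the derivation and validation data sets and leave Table 2 as it is. The cost is a sentence and a little extra analysis, with no new data and no change to the models. The one drawback is a second follow-up definition for a single descriptive series, which should be labelled where it is reported.
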